## SPECIFIC AIMS

As of 2015, 30 million Americans (9.4% of the US population) had diabetes and it was the seventh leading cause of death based on 79,535 death certificate [131]. In addition to the American Diabetes Association (ADA) reported 1.25 million people in the United States with type 1 diabetes, about 29% of the 29 million individuals with type 2 diabetes use insulin [132]. Long-term complications of hyperglycemia include retinopathy, nephropathy, neuropathy, and cardiovascular disease [133, 134]. The latest position statement by the ADA recommends a hemoglobin A1c goal of <7% in adults and <7.5% in pediatric age-groups [55, 135]. This goal challenges even the most motivated, knowledgeable and socioeconomically privileged patient. Despite a \$327 billion investment in diabetes healthcare in 2017, nearly half of those with diabetes have a hemoglobin A1c above goal [136] and 31% have a hemoglobin A1c >9% [131].

Insulin replacement treatment is a significant burden with a narrow therapeutic margin, too much insulin results in acutely debilitating hypoglycemia and too little causes hyperglycemia that, over years, results in microvascular and coronary artery disease. In 2016, following years of clinical trials performed at Stanford and other centers, the FDA approved the Medtronic 670G "hybrid" closed-loop system which automatically controls insulin delivery based on continuous glucose monitor (CGM) data [137]. Unfortunately, current subcutaneous insulin pharmacokinetics are too slow to provide meal coverage without announcement and the kinetics make it necessary to choose between hypoglycemia and hyperglycemia prevention, inevitably generating alarms when the user hits the opposite extreme [138]. Additionally, there are many who stop using CGM or insulin pumps; these reasons for discontinuation include: alarms, trust in the technology and dislike of wearing devices [102]. An implanted "invisible" pump could deliver intraperitoneal insulin with more rapid pharmacokinetics providing full closed-loop glucose control and thereby reduce the burden and morbidity of diabetes.

Prior investigation of intravenous and intraperitoneal automated insulin delivery technology were limited by the absence of practical, accurate CGM technology. Consequently, these approaches were erroneously discarded. CGM, catheter and insulin pump technology continue to evolve rapidly, but the optimal location of insulin delivery for full closed-loop control remains unknown. *We posit that long-term intraperitoneal insulin delivery will be more physiologic with multiple benefits including improved body composition and BMI (important additional cardiovascular risk factors), bone health and user experience while at the same time providing the necessary kinetics and glucagon response for fully automated insulin delivery.* Intraperitoneal insulin delivery will be simulated from available data with assessment of multiple control strategies.

**AIM 1: To identify unique benefits of long-term intraperitoneal insulin use.** Utilizing data being collected from [name] (co-mentor) cohort of intraperitoneal users with type 1 diabetes, we will evaluate body composition, bone health and human factors compared to matched controls using subcutaneous insulin. Hypothesis 1: Long-term intraperitoneal use is associated with decreased BMI, body fat percentage and visceral adiposity with improved markers of bone health, and more positive opinions of diabetes technology.

**AIM 2: To describe the pharmacokinetics and compare glucagon response to hypoglycemia of novel insulin formulations delivered via upper peritoneal, lower peritoneal and subcutaneous routes.**

[figure not shown]
Hypothesis 2: Pharmacokinetics of intraperitoneal insulin will be faster and lead to greater counter-regulatory glucagon response than subcutaneous insulin. Upper peritoneal delivery will be faster than lower peritoneum.

**AIM 3: To use available intraperitoneal pharmacokinetic and counter-regulatory data to perform *in silico* modeling and test performance with various control strategies.** The optimal algorithm will be the least computationally demanding that provides glycemic control in range (70-180mg/dL) over a variety of physiologic conditions.

Hypothesis 3: With more rapid pharmacokinetics we can utilize more straightforward control strategies to achieve >90% time in range.

This work will deliver a greatly needed control strategy for intraperitoneal insulin delivery that allows for full closed-loop glucose control. Our results will help guide the development of an implanted insulin pump being developed by PhysioLogic Devices (**Figure 1**). An efficient control algorithm will be needed to run on an embedded microcontroller with limited power. The goal of our combined efforts will be multi-center human clinical trials to achieve full closed-loop, reducing the burden of diabetes, and achieving optimum glycemic control.

**Research Design:** This will be a descriptive pharmacokinetic study of upper and lower versus subcutaneous Fiasp, with assessment of glucagon response to insulin-induced hypoglycemia. 15 healthy adult participants with type 1 diabetes on insulin pump and continuous glucose monitor will be consented and asked to come in for three visits separated by at least one week. Before any other invasive procedure the abdominal area will be assessed by an experienced interventional radiologist with gray-scale and color Doppler ultrasound to determine the safest puncture site (**Figure 3**). Gray-scale sonography will be used to find the area that provides the most separation between the anterior abdominal wall and the bowel loops. If the experienced interventional radiologist feels no safe area exists, the subject will be excluded.

[figure not shown]
Participants will fast overnight and suspend subcutaneous insulin delivery approximately 1 hour prior to each procedure. For the first two visits, participants will be randomized to either upper or lower peritoneal injection. An IV will be inserted for blood draws for YSI glucose, insulin, and glucagon levels. Another IV will be placed for dextrose administration. Color Doppler sonography of the puncture site will be performed to visualize the epigastric vessels and verify they are at least 1 cm away from the determined puncture site. Under sonographic guidance, a 22-gauge needle is inserted at the selected site with the needle angled 45° caudally. Real-time

visualization of the needle insertion through the subcutaneous tissue, rectus abdominis muscle, and peritoneum will be performed. The peritoneum is seen as an echogenic line just deep in relation to the rectus abdominis muscle fibers. The needle will be taken to the edge of this echogenic line which may be associated with minimal momentary discomfort [239]. Approximately 0.25 units/kg Fiasp will be administered through the needle and the needle removed. Following injection, blood collection and measures will occur every 5 minutes for either 150 minutes or until glucose concentration has a stable trend. A 10% dextrose bolus of 2.5mL/kg will be provided following a blood sugar reading  $\leq 50\text{mg/dL}$ . After 150 minutes have elapsed or glucose remains stable within 10mg/dL for 2 time points, the patient will resume their home insulin regimen. Data from the patient's CGM will be downloaded.

At least one week from the last peritoneal injection a similar subcutaneous procedure will take place. An IV will be inserted for blood draws for YSI glucose, insulin, and glucagon levels. Another IV will be placed for dextrose administration. Approximately 0.2 units/kg Fiasp will be administered by subcutaneous injection. Following injection, blood collection and measures will occur every 15 minutes for 6 hours or until glucose is stable. A 10% dextrose bolus of 2.5mL/kg will be provided following a blood sugar reading  $\leq 50\text{mg/dL}$ . After 6 hours have elapsed or glucose remains stable within 10mg/dL for 2 time points, the patient will resume their home insulin regimen. Data from the patient's CGM will be downloaded. See **Figure 4** for study diagram.

**Figure 4.** SA2 Study Diagram

**Statistical Considerations and Power Analysis:** Using analyses appropriate for paired measures, we will employ paired t-tests or the analogous non-parametric test (e.g., Wilcoxon signed-rank) to assess differences in pharmacokinetic features between delivery mechanisms. In the prior 2000 study by Oskarsson and colleagues, 7

subjects with longstanding type 1 diabetes receiving subcutaneous and intraperitoneal insulin underwent induced hypoglycemia with IV insulin and had glucagon measured at baseline and during hypoglycemia [1]. The maximal glucagon response subtracted from baseline was  $7.5 \pm 3.0 \text{ pg/mL}$  on subcutaneous insulin and  $17.0 \pm 3.1 \text{ pg/mL}$  on intraperitoneal insulin. Assuming a type I error rate of 0.05, 15 individuals will provide  $>90\%$  power to detect an effect size of 1.0 (maximal change in glucagon of 3.0).

**Expected Outcomes:** We will test if there is a significant difference in glucagon response during hypoglycemia between intraperitoneal and subcutaneous administration. A mean pharmacokinetic curve will be generated from the above data for upper/lower intraperitoneal and subcutaneous insulin administration. We anticipate that intraperitoneal Fiasp will have faster pharmacokinetics than subcutaneous delivery, and that intraperitoneal delivery will result in a more significant counter-regulatory glucagon response. The upper peritoneal pharmacokinetic profile may be more rapid than lower peritoneal delivery.

**Potential Pitfalls & Alternative Strategies:** There has been only 1 reported case of inadvertent bowel puncture with ultrasound guidance, occurring after the probe was removed and the needle unintentionally advanced. The patient received antibiotics and had no clinical sequelae [240]. We are deeply vested in the safety of our human subjects. All invasive procedures will be performed by an experienced interventional radiologist. To avoid this specific complication we will only take the needle tip to the edge of the visceral peritoneum, use a smaller needle and continue ultrasound recording until the needle is removed. The procedure to access the intraperitoneal space is derived from that used to place intraperitoneal catheters for peritoneal dialysis. An alternative procedure would be to perform the study in those with existing peritoneal catheters. Subjects with peritoneal dialysis catheters likely have impaired renal clearance or have recently received kidney transplant, which would alter pharmacokinetics. We have chosen not to use existing intraperitoneal pump users since prolonged suspension of insulin delivery may increase the risk of occlusions. We use Fiasp as it is the fastest subcutaneous insulin available. 1-hour suspension reduces plasma insulin with low risk of ketosis [241].

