#### 4.2. Study Design

##### 4.2.a. Narrative Study Description

15 healthy adult participants with type 1 diabetes on insulin pump and continuous glucose monitor will be consented and asked to come in for three visits separated by at least one week. Before any other invasive procedure, the abdominal area will be assessed by an experienced radiologist with gray-scale and color Doppler ultrasound to determine the safest puncture site. Gray-scale sonography will be used to find the area that provides the most separation between the anterior abdominal wall and the bowel loops. If the radiologist feels no safe area exists, the subject will be excluded.

Participants will fast overnight and suspend subcutaneous insulin delivery 3 hours prior to each procedure. For the first two visits, participants will be randomized to either upper or lower peritoneal injection. An IV will be inserted for blood draws for YSI glucose, insulin, and glucagon levels. Another IV will be placed for dextrose administration. Color Doppler sonography of the puncture site will be performed to visualize epigastric vessels and verify that they are at least 1cm away from the determined puncture site. Under sonographic guidance, a 22-gauge needle is inserted at the selected site with the needle angled 45° caudally. Real-time visualization of the needle insertion through the subcutaneous tissue, rectus abdominis muscle, and peritoneum will be performed. The peritoneum is seen as an echogenic line just deep in relation to the rectus abdominis muscle fibers. The needle will be taken to the edge of this echogenic line which may be associated with minimal momentary discomfort. Approximately 0.25u/kg Fiasp will be administered through the needle and the needle removed. Following injection, blood collection and measures will occur every 5 minutes for 150 minutes or until glucose stabilizes. A 10% dextrose bolus of 2.5ml/kg will be provided following a blood sugar reading  $\leq$  50mg/dl. After 150 minutes have elapsed or glucose remains stable within 10mg/dl for 2 time points, the patient will resume their home insulin regimen. Data from the patient's CGM will be downloaded.

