At least one week from the last peritoneal injection a similar subcutaneous procedure will take place. An IV will be inserted for blood draws for YSI glucose, insulin, and glucagon levels. Another IV will be placed for dextrose administration. Approximately 0.25 units/kg Fiasp will be administered by subcutaneous injection. Following injection, blood collection and measures will occur every 15 minutes for 6 hours or until glucose stabilizes. A 10% dextrose bolus of 2.5ml/kg will be provided following a blood sugar reading  $\leq$  50mg/dl. After

4 hours have elapsed and glucose remains stable within 10mg/dl for 2 time points, the patient will resume their home insulin regimen. Data from the patient's CGM will be downloaded.

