## STATISTICAL DESIGN AND POWER

Using analyses appropriate for paired measures, we will employ paired t-tests or the analogous non-parametric test (e.g., Wilcoxon signed-rank) to assess differences in pharmacokinetic features between delivery mechanisms. In the prior 2000 study by Oskarsson and colleagues, 7 subjects with longstanding type 1 diabetes receiving subcutaneous and intraperitoneal insulin underwent induced hypoglycemia with IV insulin and had glucagon measured at baseline and during hypoglycemia. The maximal glucagon response subtracted from baseline was  $7.5 \pm 3.0 \text{ pg/ml}$  on subcutaneous insulin and  $17.0 \pm 3.1 \text{ pg/ml}$  on intraperitoneal insulin. Assuming a type I error rate of 0.05, 15 individuals will provide  $>90\%$  power to detect an effect size of 1.0 (maximal change in glucagon of 3.0).

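### The subcutaneous dose is given as both 0.2 and 0.25 units/kg; under the lower figure, dose changes together with route in every participant

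*Combined protocol and SAP*

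**What the plan says.** Two current descriptions of the same study sit in the document: the Aim 2 Research Design and the Section 4.2.a narrative.

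- **Subcutaneous dose.** Aim 2: "Approximately 0.2 units/kg Fiasp will be administered by subcutaneous injection". Section 4.2.a: "Approximately 0.25 units/kg Fiasp will be administered by subcutaneous injection".
- **Intraperitoneal dose.** Aim 2: "Approximately 0.25 units/kg Fiasp will be administered through the needle and the needle removed". Section 4.2.a: "Approximately 0.25u/kg Fiasp will be administered through the needle and the needle removed". These agree.
- **Pump suspension.** Aim 2: "Participants will fast overnight and suspend subcutaneous insulin delivery approximately 1 hour prior to each procedure". Section 4.2.a: "Participants will fast overnight and suspend subcutaneous insulin delivery 3 hours prior to each procedure".
- **Ketosis justification.** Potential Pitfalls & Alternative Strategies supports a 1-hour suspension, with a citation. Potential Risks also gives reassurance about ketoacidosis but states no duration.
- **Analysis.** Statistical Design and Power, like the matching Aim 2 paragraph, plans paired t-tests or Wilcoxon signed-rank tests "to assess differences in pharmacokinetic features between delivery mechanisms". Neither mentions a dose term or dose normalisation.
- **Outcomes.** Section 4.3 makes glucagon response to induced hypoglycemia primary and descriptive pharmacokinetics secondary, each measured under all three routes.

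**The concern.** Staff cannot follow both texts on the subcutaneous dose, and the document does not say which prevails. Nothing shows that unequal doses were intended: no rationale is given, and Aim 2 presents the subcutaneous visit as a similar procedure.

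The comparison of intraperitoneal with subcutaneous delivery is the main question. Under the Aim 2 text, each participant's route contrast is also a dose contrast. Pairing removes differences between people, but it cannot remove a dose difference that is the same in everyone. Any exposure measure that depends on dose would then show a route difference that is partly a dose difference. The glucagon response could also be affected, because dose can change how fast glucose falls and whether the hypoglycemic threshold is reached.

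The suspension conflict is a separate matter. Each text applies its suspension time to all three visits, so it does not itself confound route. The 3-hour text lacks a justification matched to its duration, and if the two texts were mixed across visits, starting conditions would differ.

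**Working it through.** **Stated power.** For a paired t-test with n = 15, effect size 1.0 and two-sided alpha 0.05 (14 df, noncentrality 1.0 × √15 = 3.87), power is 94.9%. This agrees with the plan's figure of more than 90%. The concern does not dispute it.

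**Dose ratio** (subcutaneous / intraperitoneal, nominal units/kg):

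| Text | Subcutaneous | Intraperitoneal | Ratio |
|---|---|---|---|
| Aim 2 Research Design | 0.20 | 0.25 | 0.80 |
| Section 4.2.a | 0.25 | 0.25 | 1.00 |

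Dosing is per kg and every participant has all three visits, so body weight cancels and the ratio applies to everyone. In units under the Aim 2 text, at assumed weights:

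- 60 kg: 0.20 × 60 = 12 subcutaneous vs 0.25 × 60 = 15 intraperitoneal
- 90 kg: 0.20 × 90 = 18 subcutaneous vs 0.25 × 90 = 22.5 intraperitoneal

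**Effect on exposure under the Aim 2 text.** Assume exposure scales as dose^b (b is not in the documents):

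- b = 0.8: 0.80^0.8 = 0.837, 16% lower
- b = 1.0: 0.800, 20% lower
- b = 1.2: 0.80^1.2 = 0.765, 23% lower

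**Illustration: chance of declaring a route difference when none exists.** Assume no true route effect on exposure, a two-sided 5% paired t-test on log exposure, n = 15, and a within-participant CV of 20%, 30% or 40% (not in the documents). The shift is b × |ln 0.80| = b × 0.223. The SD of the paired difference is √(2 ln(1 + CV²)), and d = shift / SD. The rejection probability comes from the noncentral t distribution with 14 df and noncentrality d√15. At b = 1:

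| CV | SD | d | P(reject) |
|---|---|---|---|
| 20% | 0.280 | 0.797 | 82% |
| 30% | 0.415 | 0.537 | 49% |
| 40% | 0.545 | 0.410 | 32% |

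Over the full assumed ranges of b and CV, the probability runs from 22% (b = 0.8, CV 40%) to 93% (b = 1.2, CV 20%).

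**What is not affected.** The upper versus lower peritoneal comparison has equal doses in both texts. Measures of speed such as time to peak would not shift if exposure is proportional to dose. The documents give no basis for putting a number on the glucagon effect.

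**The case against.** The contradictions themselves are not in dispute. The strongest case is against what is built on them.

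- **Endpoint.** The rejection rates apply to log exposure, but the plan names no exposure measure. Pharmacokinetics is secondary and descriptive, and the pharmacokinetic hypothesis concerns speed. This stands: the rates are illustrative, do not bear on the primary outcome, and span 22% to 93% depending on inputs outside the documents. The finding does not rest on them.
- **Unequal doses may be deliberate.** Section 4.3 asks for enough insulin to produce hypoglycemia, not for matched units. That is possible, but then Section 4.2.a is wrong and a rationale is missing. A correction is needed either way.
- **Data already collected.** Sources of Materials lists insulin doses and visit dates, so dose-normalisation needs no new data. This stands; only the suspension time would be a new item to record.
- **Equal doses would not isolate route.** The subcutaneous visit is always last and is sampled every 15 minutes rather than every 5. This is true and is a further limitation. The different intervals also mean that giving dextrose at 50 mg/dL or below on every visit only partly limits differences in the depth of hypoglycemia.
- **A further conflict at the same visit.** Aim 2 lets home insulin resume after 6 hours or once glucose is stable; Section 4.2.a requires 4 hours and stable glucose. This adds to the finding.

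None of these points resolves the conflict over dose.

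**Conclusion.** The concern holds and must be fixed. The two current texts give different subcutaneous doses, and the word approximately cannot reconcile them because it precedes both figures. The size that follows from the documents alone is a dose ratio of 0.80 under one text and 1.00 under the other. Confounding of dose with route arises only if the Aim 2 text is followed; it then affects every participant and the planned tests do not address it. The 16% to 23% fall in exposure rests on the assumed scaling exponent. The rejection rates rest further on the assumed CVs and on no true route effect. The suspension conflict (about 1 hour versus 3 hours) is real but does not itself confound route.

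**What to change.** - Reconcile the Aim 2 Research Design and Section 4.2.a to a single subcutaneous dose. The investigators choose the value.
- Reconcile the suspension time across Aim 2, Potential Pitfalls & Alternative Strategies and Section 4.2.a, with a justification that matches the duration kept.
- In the same amendment, reconcile the rule for ending the subcutaneous visit.
- If doses are to differ by route, state the reason, dose-normalise any exposure measure compared between routes, and do not attribute a glucagon difference to route alone.
- If any visits have already been run, record for each one which text was followed, with the dose and suspension time actually used.

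The cost is one wording amendment, with no extra participants, visits or samples. The Study Timeline gives only planned dates, so the documents do not show whether the record of past visits is needed.

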## Section 2 - Study Population Characteristics (Study 1)

### 2.1. Conditions or Focus of Study

- Type 1 Diabetes Mellitus

### 2.2. Eligibility Criteria

#### Eligibility Criteria

To be eligible for the study, a subject must meet the following criteria:

1. 18-60 years of age
2. Clinical diagnosis of type 1 diabetes
3. On insulin pump therapy and continuous glucose monitor (CGM) for at least 3 months
4. Ability to safely receive intraperitoneal injection
5. For females, not currently known to be pregnant
6. Understanding and willingness to follow the protocol and sign informed consent
7. Ability to speak, read and write in the language of the investigators

#### Exclusion Criteria

The presence of any of the following is an exclusion for the study:

1. Diabetic ketoacidosis in the past 3 months
2. Severe hypoglycemia resulting in seizure or loss of consciousness within 3 months prior to enrollment
3. Pregnant or lactating
4. Active infection
5. A known medical condition that in the judgment of the investigator might interfere with the completion of the protocol
6. Known cardiovascular events in the last 6 months
7. Known seizure disorder
8. Inpatient psychiatric treatment in the past 6 months
9. Lack of stability on medication 1 month prior to enrollment including antihypertensive, thyroid, anti-depressant or lipid lowering medication.
10. Suspected drug or alcohol abuse
11. Chronic kidney disease (GFR < 60 mL/min/1.73mA2)

